## **3. Statistical analysis plan**

Data analyses will be performed using the Statistical Package for Social Sciences (SPSS), version 24.0 (IBM Corporation, Armonk, NY, USA).

Descriptive statistics [means  $\pm$  standard deviations (SD) and relative frequencies (%)] will be retrieved. Pearson correlations will be used to assess correlations between the outcome variables. Chi-squared tests will be applied to determine group differences of injury prevalence and the occurrence of severe, respectively mild injury events. Multivariate logistic regressions will be performed to evaluate predictive factors among the outcome variables (independent variables) of severe injury events (dependent variable; no severe injury = 0 versus severe injury = 1) in elites and amateurs separately. Independent samples t-tests will be used to evaluate mean group differences in demographics, and training and injury related variables between the elite and the amateur mountain bikers. P-values  $< 0.05$  will be considered as statistically significant. According to Cohen (1992), effect sizes will be calculated for the correlation analyses and defined as follows;  $r = 0.20$  small,  $r = 0.50$  medium,  $r = 0.80$  strong.

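### The cut-offs for labelling correlations (0.20, 0.50, 0.80) are the conventional scale for a standardised mean difference, so much of the range of r would be labelled one grade too weak

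*Combined protocol and SAP*

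**What the plan says.** All the relevant text is in section 3 of the combined protocol and SAP.

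- On the statistic: "Pearson correlations will be used to assess correlations between the outcome variables".
- On grading it: "effect sizes will be calculated for the correlation analyses and defined as follows". Three values of r follow: 0.20 (small), 0.50 (medium) and 0.80 (strong). The sentence credits a published effect-size source and gives no study-specific reason for the values.
- On the elite–amateur comparison of means: "Independent samples t-tests will be used to evaluate mean group differences in demographics, and training and injury related variables". No effect size or grading scale is set for these tests.
- On significance: p-values under 0.05 "will be considered as statistically significant". This rule is separate from the effect-size labels.

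No other part of the document gives a different grading rule. The plan does not say whether the three values are lower bounds of bands or reference points, or what a correlation below 0.20 is to be called.

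**The concern.** The values 0.20, 0.50 and 0.80 coincide exactly with the usual small, medium and large marks for d. That is the effect size that would go with the t-tests, for which the plan sets no scale. A correlation is bounded by 1 and d is not, so the same number means very different things on the two scales. Marks made for d are demanding when applied to r.

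What is at stake is how the associations are described. The study's aim (section 1) is descriptive, and a reader of a survey report may rely on the adjective as much as on the coefficient. A correlation of 0.45 between, say, training hours and number of injuries would be called small if the cut-offs are lower bounds, and one of 0.15 would have no label. Any error runs in one direction, towards understatement.

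**Working it through.** **Inputs**

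- Plan's cut-offs for r: 0.20, 0.50, 0.80 (section 3).
- Conventional marks for d: 0.2, 0.5, 0.8. Assumption: general convention, not in the documents.
- Conventional marks for r: 0.10, 0.30, 0.50. Assumption: general convention, not in the documents. The cited source was not available for this review.
- Elite-to-amateur split: not in the documents. Equal groups and an 80/20 split are shown as a range.

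**Step 1. Can the plan's figures be reproduced as marks for r?** The plan shows no derivation. The values equal the d marks unconverted. For two groups with proportions p and 1 − p, the conversion is r = d / √(d² + 1/(p(1 − p))). With equal groups this is r = d / √(d² + 4); with an 80/20 split, 1/(0.8 × 0.2) = 6.25 replaces 4.

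| d | r, equal groups | r, 80/20 split |
|---|---|---|
| 0.2 | 0.2/√4.04 = 0.0995 | 0.2/√6.29 = 0.0797 |
| 0.5 | 0.5/√4.25 = 0.2425 | 0.5/√6.50 = 0.1961 |
| 0.8 | 0.8/√4.64 = 0.3714 | 0.8/√6.89 = 0.3048 |

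Neither variant gives 0.20, 0.50 and 0.80.

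**Step 2. What do the plan's cut-offs demand?** The inverse with equal groups is d = 2r / √(1 − r²), and shared variance is r².

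| r in the plan | Label | Equivalent d | r² |
|---|---|---|---|
| 0.20 | small | 0.41 | 0.04 |
| 0.50 | medium | 1.15 | 0.25 |
| 0.80 | strong | 2.67 | 0.64 |

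A strong correlation must therefore share 64% of variance, against 25% if the top mark were 0.50.

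**Step 3. Which labels change?** Both sets are read as lower bounds, and the top grade (strong or large) is treated as the same.

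| \|r\| | Plan | Marks 0.10/0.30/0.50 | Difference |
|---|---|---|---|
| below 0.10 | none | none | same |
| 0.10–0.19 | none | small | one grade lower |
| 0.20–0.29 | small | small | same |
| 0.30–0.49 | small | medium | one grade lower |
| 0.50–0.79 | medium | large | one grade lower |
| 0.80 or above | strong | large | same |

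The affected bands cover 0.10 + 0.20 + 0.30 = 0.60 of the |r| scale. This is a share of the scale, not of the correlations the survey will find. No value is graded too high.

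**Step 4. Does the result depend on the assumed r marks?** Using the equal-groups conversions from step 1 (0.10, 0.24, 0.37) instead, about 66% of the scale drops at least one grade, and values from 0.372 to 0.499 drop two. Again nothing is graded too high.

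**Step 5. Does it depend on reading the marks as lower bounds?** Suppose each r takes the label of the nearest mark. The plan's boundaries are then (0.20 + 0.50)/2 = 0.35 and (0.50 + 0.80)/2 = 0.65. Those of the assumed r marks are (0.10 + 0.30)/2 = 0.20 and (0.30 + 0.50)/2 = 0.40. Correlations between 0.20 and 0.35, and between 0.40 and 0.65, would still be labelled one grade lower. The bands move, but the direction does not.

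**The case against.** Verbal grades for a correlation are conventions, and a study may prespecify a stricter scale. The replacement marks are not in the documents and the cited source could not be consulted, so one could say that the review merely prefers another threshold. Part of this stands: 0.10, 0.30 and 0.50 must be labelled as an assumption, and the bands in step 3 rest on it. But the plan does not present its values as a deliberate stricter choice. It takes them from a general effect-size source, gives no reason, and they match the scale of a different statistic exactly. The conversion in step 1 shows that they are too high for r without using the assumed r marks, though it does assume the convention for d.

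The plan also does not say that its values are lower bounds, nor that r below 0.20 means no effect. That stands too. On a nearest-mark reading, 0.45 would be medium under the plan, not small. Step 5 shows that the understatement remains, in different bands.

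A reader might infer stronger things that the documents do not support:

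- *That every correlation will be graded too weak.* Under the assumptions of step 3, values below 0.10, from 0.20 to 0.29, and at or above 0.80 keep their label.
- *That the study's findings on risk are compromised.* The labels apply to the correlations only. Predictors of severe injury are assessed by logistic regression and group differences by chi-squared and t-tests; none of these uses the cut-offs, and neither does the significance rule.
- *That leaving out d beside the t-tests is an error.* The plan does not promise it, and adding it is a reporting choice.

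**Conclusion.** The point holds as a wrongly specified grading rule: the plan applies to Pearson r a scale that by convention belongs to d, and gives no reason of its own. Followed as written, the rule can only understate the strength of correlations relative to the usual marks. The understatement is one grade over 0.10–0.19, 0.30–0.49 and 0.50–0.79. This size rests on two assumptions: that 0.10, 0.30 and 0.50 are the appropriate marks for r, and that the cut-offs act as lower bounds. The direction survives both alternatives tested. The consequence is confined to descriptive wording, so this is a small correction, but one worth making before the results are written up.

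**What to change.** In section 3, choose one of two wordings.

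1. Replace the cut-offs with ones meant for r: 0.10 small, 0.30 medium and 0.50 large. State that they are lower bounds on |r| and that values below 0.10 are not labelled.
2. If 0.20, 0.50 and 0.80 are kept, declare them as the study's own stricter scale, give the reason, say how values between and below them are labelled, and remove the attribution to the cited source.

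Whichever is chosen, report r itself next to its label. Optionally, report d beside each elite–amateur t-test and keep 0.2, 0.5 and 0.8 for that; it follows from the planned means and SDs together with the group sizes.

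The cost is one sentence of SAP wording. No new data are needed and no other analysis changes.

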## Mountain biking Injury Questionnaire

*Thank you for agreeing to take part in this important questionnaire about mountain biking injuries. The information we can obtain from this survey may help to improve the knowledge about injury prevalence in mountain biking. With this knowledge, it may be possible to improve safety in future and prevent injury.*

*Be assured that all answers you provide will be kept in the strictest confidentiality. This survey is anonymous. Do not write your name on the survey.*

*Please tick only the most correct answer.*

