## **2. Methods**

A survey (as outlined below) of mountain biking related injuries will be conducted on the participants of the Swiss Epic mountain bike event in 2017 held in Valais. The retrospective questionnaire is designed in accordance with existing literature ((Gaulrapp et al., 2001; Lareau and McGinnis, 2011), will include 25 questions and will be translated into English, French, Italian, Spanish and German. The participants will be asked to tick the most appropriate answer. The questionnaire aims to assess the athletes' 1) basic demographics, riding level and years of experience, 2) number of races per year and mean hours of training per week, 3) number and kind of suffered injuries related to mountain biking and medical treatment requirement, 4) and amount and kind of protective gear items.

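### The form is framed only around injuries and the plan provides for no denominator or response rate, so over-representation of injured riders is plausible and cannot be assessed

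*Combined protocol and SAP*

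**What the plan says.** The form is headed "Mountain biking Injury Questionnaire". Its introduction begins "Thank you for agreeing to take part in this important questionnaire about mountain biking injuries" and gives the rider this purpose: "The information we can obtain from this survey may help to improve the knowledge about injury prevalence in mountain biking". The rest concerns safety, injury prevention and confidentiality. No line addresses riders with no injury to report. The form also states: "This survey is anonymous. Do not write your name on the survey".

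Section 2 (Methods) says that the survey "will be conducted on the participants of the Swiss Epic mountain bike event in 2017 held in Valais". It gives no number of participants and does not say how riders are approached, how forms are distributed or how returns are counted.

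Section 3 (Statistical analysis plan) provides for means, standard deviations and percentages, and then says: "Chi-squared tests will be applied to determine group differences of injury prevalence and the occurrence of severe, respectively mild injury events". It names no response rate, no comparison of respondents with the event field and no sensitivity analysis for non-response.

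The form records gender, date of birth and race format. Question 9 asks for the number of injuries, so a never-injured rider can enter 0.

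**The concern.** A prevalence computed on returned forms estimates the prevalence in the field only if the decision to respond is unrelated to having been injured. Taking part is voluntary, and a form that speaks only of injuries gives a never-injured rider reason to think it is meant for someone else. Riders who decline for that reason drop out of the denominator, and prevalence rises.

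The group comparison is exposed as well. If the link between injury and response differs between elite and amateur riders, the chi-squared test can show a difference that reflects response alone.

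Because the form is anonymous, non-responders cannot be followed up by name afterwards. Any safeguard has to be in place before forms are handed out.

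**Working it through.** The documents state no expected prevalence, sample size, field size or response rate, so there is no figure of the plan's own to reproduce. Everything below is illustrative.

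**Step 1. Bias in the observed prevalence.** Let p be the true prevalence among eligible riders, taken here as the share with at least one injury at question 9. Let k be the response rate of injured riders divided by that of never-injured riders. The observed prevalence is

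q = p·k / (p·k + 1 − p),

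which is the same as multiplying the true odds by k. Both p and k are assumed. The ratios 1.2, 1.5 and 2 correspond, for example, to 60% response in injured riders against 50%, 40% and 30% in the never-injured.

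| True p | k = 1.2 | k = 1.5 | k = 2 |
|---|---|---|---|
| 40% | 0.48/1.08 = 44.4% | 0.60/1.20 = 50.0% | 0.80/1.40 = 57.1% |
| 60% | 0.72/1.12 = 64.3% | 0.90/1.30 = 69.2% | 1.20/1.60 = 75.0% |
| 90% | 1.08/1.18 = 91.5% | 1.35/1.45 = 93.1% | 1.80/1.90 = 94.7% |

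The 90% row matters. Question 9 has no time window, and question 12 allows injuries that needed no treatment, so a high lifetime prevalence is quite possible. The error is then about 2 to 5 percentage points, against about 4 to 17 in the other two rows.

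**Step 2. The reverse direction.** With k = 0.8, a true 50% is observed as 0.40/0.90 = 44.4%, and a true 70% as 0.56/0.86 = 65.1%.

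**Step 3. The group comparison.** Suppose k = 1.5 in amateurs, k = 1 in elites, and the true prevalence is equal in both. At a true 60%, the survey shows 69.2% against 60%, a false difference of 9 points. At a true 90%, it shows 93.1% against 90%, a false difference of 3 points. In both cases the spurious odds ratio is 1.5/1 = 1.5. Nothing in the documents says that response is selective in one group only; this shows the mechanism, not an expected result.

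**Step 4. What a denominator would buy.** Let R be forms returned divided by eligible riders. If no non-responder was injured, the field prevalence is qR. If every non-responder was, it is qR + (1 − R). The overstatement is therefore at most q(1 − R). For an assumed q = 70%:

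| R | Lower bound qR | Upper bound qR + (1 − R) | Maximum overstatement |
|---|---|---|---|
| 30% | 21% | 91% | 49 points |
| 50% | 35% | 85% | 35 points |
| 70% | 49% | 79% | 21 points |
| 90% | 63% | 73% | 7 points |

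The bounds need only the field size and the number of returns. They are wide at low response and useful at high response, but the plan provides for neither count.

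**The case against.** The strongest reply is that selective response is only inferred. The opening sentence thanks someone who has already agreed, so it may be read after the decision to take part, and the invitation itself is not in the available text. Prevention is a purpose that a never-injured rider may share. Questions 1 to 8 and 19 to 25, which make 15 of the 25, concern experience, training, gear, pain not due to injury, and product use, and such a rider can answer them. The aim in the Introduction is to describe how injuries arise and what follows from them. Mechanism, body location and recovery among injured riders are not distorted when never-injured riders decline.

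Most of this stands, and it limits the claim. It does not remove it: prevalence is the purpose told to riders and a tested quantity, and nothing in the plan would show whether response was selective.

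Three stronger readings are tempting, and the documents do not support them:

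- A reader might infer that no count of forms is kept. The documents are silent on this; they do not provide for a count.
- A reader might infer that prevalence is overstated. There are no response data, and Step 2 of the working shows that the sign depends on k.
- A reader might infer that the error cannot be bounded. The frame is one event with a finite field, so the bounds in Step 4 apply once the field size is known.

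**Conclusion.** The point holds as a gap in design and reporting, not as a demonstrated bias. The heading and introduction speak only of injuries, no line invites never-injured riders, and the plan provides for nothing by which response could be measured.

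The possible size depends on two unknowns. Under response ratios of 1.2 to 2, the overstatement is about 4 to 17 points at a true prevalence of 40%, about 4 to 15 points at 60%, and about 2 to 5 points at 90%. With a ratio below 1, prevalence is understated. All of these ratios and prevalences are assumptions.

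The change is worth making before fielding because it is cheap, concerns a tested quantity, and is hard to make up for once anonymous forms have been collected. It does not call into question the description of injuries among those who report one.

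**What to change.** 1. Add one line under the title in all five languages: *Please complete this form even if you have never been injured.* A neutral title is optional.
2. Record the number of eligible participants, forms issued and forms returned, each by race format. Forms issued separates riders who were never offered a form from those who declined.
3. Report the response rate overall and by race format, and give prevalence with the worst-case bounds qR to qR + (1 − R).
4. Add a sensitivity range that lets response differ in either direction. Inverting the formula in Step 1 gives p = q / (q + k(1 − q)). For example, an observed 70% corresponds to 0.70/1.30 = 53.8% at k = 2 and 0.70/0.85 = 82.4% at k = 0.5. For the elite–amateur comparison, let k differ between the groups.
5. If the organiser can supply entry totals by race format and gender, compare respondents with them as a description. Do not present post-stratification on these factors as a remedy: within each cell, response that depends on injury stays uncorrected.

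The cost is one sentence to translate, a tally sheet, a request to the organiser for field totals, and a prevalence reported with wider stated uncertainty. No new question is needed.

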**7. How many races per year**

\_\_\_\_\_

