**8. Protective gear**

helmet       gloves       eyewear       upper armour       lower armour

other \_\_\_\_\_

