**9. Number of injuries obtained during mountain biking**

\_\_\_\_\_

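### The one-tick instruction stops Question 8 from measuring how much protective gear riders wear, and caps its item percentages at a 100% total

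*Combined protocol and SAP*

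**What the plan says.** Section 2 (Methods) names four things the questionnaire is to assess. The last is the "amount and kind of protective gear items". The same section gives the answering rule: "The participants will be asked to tick the most appropriate answer". The header of the Mountain biking Injury Questionnaire puts it more strictly: "Please tick only the most correct answer".

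Gear appears in one place only, Question 8, headed "Protective gear". It offers gloves, a helmet, eye protection, armour for the upper and for the lower body, and a write-in 'other'. It carries no instruction of its own, no field for a number and no 'none' box.

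Two other counts named in Section 2 do have a space for a number: Question 7 ("How many races per year") and Question 9 ("Number of injuries obtained during mountain biking"). Question 12 shows that the authors add a local instruction when they want one, because it tells riders with several injuries to answer for the worst.

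Section 3 (Statistical analysis plan) says that means, SDs and "relative frequencies (%)] will be retrieved". It gives no coding for questions with several answers.

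**The concern.** The items in Question 8 are not alternatives, since a rider can wear most or all of them on the same ride. A one-answer rule turns a question about what is worn into a question about which single item to name. With no count field, the amount of gear can come only from the ticks, and the rule limits those to one.

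One of the four things Section 2 wants to assess therefore cannot be supplied by a respondent who follows the form. Reported percentages would look like usage rates but would show which item riders chose to tick. The survey is anonymous, so nobody can be asked again afterwards.

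**Working it through.** The documents give no gear-use, compliance or sample-size figure, so there is nothing of the plan's to reproduce. Steps 1 to 3 need only the form. Step 4 uses assumed values and is an illustration. Step 5 looks at what Section 3 would do with the result.

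**1. Recorded count under full compliance.** Let p be the share of riders who tick one box, and count 'other' as one item. Each rider's recorded count is 0 or 1.

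- Blanks treated as missing: every count is 1, so the mean is 1 and the SD is 0.
- Blanks treated as zero: mean = p ≤ 1, and SD = √(p(1 − p)) ≤ √(0.5 × 0.5) = 0.5.

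The second treatment is itself a guess. Without a 'none' box, a blank may mean no gear or a skipped question.

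**2. Cap on the percentages.** With at most one tick per rider, the six item percentages sum to 100p ≤ 100% (exactly 100% if blanks are dropped). If two items both exceeded 50%, their sum would exceed 100%, which is impossible. As an example, suppose every rider wears a helmet, gloves and eyewear. True use is 100% for each, a sum of 300%. The recorded shares sum to 100%, an average of 100/3 = 33% each.

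**3. The error is uneven.** An item that all its wearers choose to tick loses nothing, and the loss falls on the items worn with it. A share can even be too high. With hypothetical numbers, let 80 of 100 riders wear and tick only a helmet, and let 20 wear nothing and leave the question blank. Dropping blanks gives 80/80 = 100% against a true 80%.

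**4. Size under assumed values.** Suppose each rider wears at least one item, with mean m. A fraction c follows the rule, independently of the number worn, and the rest tick everything they wear.

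- Recorded mean = c × 1 + (1 − c) × m
- Share of item-use lost = [m − c − (1 − c)m] / m = c(1 − 1/m)

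| c | m = 1 | m = 1.5 | m = 2 | m = 3 |
|---|---|---|---|---|
| 0 | 0% | 0% | 0% | 0% |
| 0.25 | 0% | 8.3% | 12.5% | 16.7% |
| 0.5 | 0% | 16.7% | 25.0% | 33.3% |
| 1 | 0% | 33.3% | 50.0% | 66.7% |

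Neither c nor m comes from the documents. Over these values the loss runs from 0% to about 67%, and nothing in the plan narrows it.

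**5. Reach into the analyses.** The t-tests address "mean group differences in demographics, and training and injury related variables", which does not name gear. The Pearson correlations and the logistic regressions for severe injury draw on a set of outcome variables that Section 3 never lists. Gear is one of the four assessed domains, so it may be among them. If it is, a count that is 1 for every compliant rider who wears any gear has almost no variance. It could not support a correlation or act as a predictor.

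**The case against.** The strongest reply is that riders faced with a list of things they wear will tick several, whatever the header says. Some may, and if all did nothing would be lost. But the form then mixes two behaviours that cannot be separated: a single tick may mean one item worn, or several with the rule obeyed. Relying on respondents to ignore the printed instruction is not a measurement plan.

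Several narrower objections stand in part:

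- Section 2 does not say 'only'. The explicit restriction is in the questionnaire header. Section 2 still describes a single answer and makes no exception for gear.
- The 'other' line is free text, so a rider could write several items there. The 0-or-1 count therefore depends on counting 'other' as one item. The cap on the percentages concerns boxes ticked and is not affected.
- Other questions also list answers that can be true together (for example Questions 3, 13, 14 and 18 to 21). Whether to relax the rule there is a separate decision. Question 8 is singled out because Section 2 states an amount of gear as something to be measured.

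A reader might infer that use of every item is under-counted. That does not follow, because one tick limits the sum of the shares and not each share (step 3). A reader might also infer that the harm is purely descriptive or, in the other direction, that the regressions are invalid. Section 3 supports neither, because it does not say whether gear enters the correlations or models. Nor does the point defeat the aim in Section 1, which concerns the causes and consequences of injury and not gear use.

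**Conclusion.** The point holds and should be fixed. The stated gear variable and the answering rule contradict each other in the current text, and nothing elsewhere in the document resolves it.

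Two consequences are certain for riders who comply: the number of items worn cannot be derived, and the six percentages cannot total more than 100%. The first assumes that 'other' counts as one item. The size of the under-count among items worn together is unknown and differs by item. It is zero if no rider complies and all tick everything they wear, or if every rider wears only one item. No figure in the documents allows a better estimate, so the percentages in the table should not be quoted as an expected loss.

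The descriptive gear results are affected. Any Section 3 correlation or regression is affected only if gear is taken as one of its outcome variables.

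**What to change.** Before data collection:

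- Change the questionnaire header and the matching sentence in Section 2 to 'tick one answer unless the question says tick all that apply'.
- Print 'tick all that apply' on Question 8 and add a 'none' box marked as exclusive.
- In Section 3, code each option yes/no. Define amount as the number of items ticked, counting each distinct item written under 'other', with 'none' as 0 and a blank as missing. Treat a form with 'none' and an item both ticked as missing for amount, and report how many there are.

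If data are already collected:

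- Report how many riders ticked more than one box on Question 8.
- Do not interpret the count as gear worn, and do not use it as a predictor.
- Label the Question 8 percentages as ticks given under a one-tick instruction.

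The cost is a few words and one box on the form in five languages, one changed sentence in Section 2, and seven yes/no columns (six options plus 'none'). No respondents or procedures are added.
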